9.6.6 Physical Examination

A complete physical examination is to be performed at each clinic visit or, if applicable, at early discontinuation from the study. Complete physical examination will include assessments of general appearance as well as the following:

- Head
- Eyes
- Ears
- Nose
- Throat
- Cardiovascular
- Dermatologic
- Lymphatic
- Respiratory
- Gastrointestinal
- Musculoskeletal

Weight will be measured with each physical examination throughout the study. Height (cm.) will be measured at screening only.

Other body systems may be examined. Clinically significant changes from baseline will be recorded as AEs

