## 10.1 Analysis Populations

The following analysis populations have been defined for this clinical study:

- a) Enrolled Population (EP): all patients who provided informed consent for this study.
- b) **Safety Population (SAF)**: the safety population consists of all subjects who are enrolled in the study and have received at least one dose of amifampridine and includes subjects who begin the Run-in period regardless of whether they are randomized to double blind medication on Day 0.
- c) Full Analysis Set (FAS): this population consists of all randomized subjects who receive at least one dose of IP (amifampridine or placebo) and have at least one post-treatment efficacy assessment. Subjects will be compared for efficacy according to the treatment to which they were randomized, regardless of the treatment actually received.
- d) **Per-Protocol Population (PPAS)**: this population is a subset of the FAS population, excluding subjects with major protocol deviations. The PPAS population will include all FAS subjects who:
  - Have no major protocol deviations or inclusion/exclusion criteria deviations that might potentially affect efficacy, and
  - Subjects who took at least 80% of the required treatment doses.

The PPAS population will be determined before database lock and unblinding subject treatment codes.

The FAS population will be the primary analysis set for all effectiveness analyses. The safety population will be used for the analysis of all safety variables and baseline characteristics. The PPAS population will be used for selected effectiveness analyses. The results obtained in PPAS population set will be seen as supportive of those obtained in the FAS population.

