### 10.2 General Statistical Considerations

The following standards will be applied for the analyses unless otherwise specified.

Simple summary statistics (descriptive statistics) for continuous data will be n (number of non-missing observations), mean, median, standard deviation, minimum, and maximum.

The frequency count and percentage will be used to summarize categorical data. Summary statistics will be presented by treatment by period and overall.

Summary statistics for all safety and efficacy variables will be presented by sequence, except for tables related to incidence of AEs which will be presented by treatment group.

All tables of baseline and demographic data will be presented by sequence.

All data collected will be presented in the by-patient data listings, sorted by patient and by period and day, where appropriate.

P-values < 0.05 will be considered as statistically significant.

95% confidence interval will be calculated as appropriate.

Change From Baseline (CFB) will be summarized for efficacy and safety assessments, where Baseline is defined as Day 0.

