**Table 1 - Categories of Severity for Adverse Events** 

Severity	Description	
Grade 1	Mild; asymptomatic or mild symptoms; clinical or diagnostic observations only; intervention not indicated.	
Grade 2	Moderate; minimal, local or noninvasive intervention indicated; limiting age-appropriate instrumental ADL*.	
Grade 3	Severe or medically significant but not immediately life-threatening; hospitalization or prolongation of hospitalization indicated; disabling; limiting self-care ADL**.	
Grade 4	Life-threatening consequences; urgent intervention indicated.	Note: Grade 4 and 5 adverse events should
Grade 5	Death related to AE.	always be reported as serious adverse events

Activities of Daily Living (ADL)

\* Instrumental ADLs refer to preparing meals, shopping for groceries or clothes, using the telephone, managing money, etc.

\*\*Self-care ADLs refer to bathing, dressing and undressing, feeding self, using the toilet, taking medications, and not bedridden.

A treatment-emergent adverse event (TEAE) is any AE that emerges after randomization having been previously absent, or worsens relative to the previous periods. All AEs will be coded using the Medical Dictionary for Regulatory Activities (MedDRA), Version 23.0. All treatment-emergent adverse events (TEAEs) will be summarized by the treatment at the time of onset. Counts and percentages will be presented by treatment for each observed system organ class (SOC) and preferred term (PT) as defined in MedDRA. A patient having more than one TEAE with the same PT in a given time period will be counted only once in the incidence calculation for that PT for that time period. Similarly, if a patient has more than one TEAE in the same SOC in a given time period, the patient will be counted only once in the total number of patients with a TEAE for that SOC for that time period. TEAEs will summarized only for the treatment at onset unless it worsens at subsequent period(s) or recurs after having resolved at a previous period; in each of these situations, the TEAE will be considered a new TEAE and summarized for both treatments.

Each TEAE will be assessed with respect to severity and relationship to treatment. The relationship of an AE will be recorded using the specified relationship categories described in Table 2.

Table 2 - Description of relationship to adverse events categories

Relationship	
Category	Description
Not Related	Exposure to the IP has not occurred
	OR

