	The administration of the IP and the occurrence of the AE are not
	reasonably related in time
	OR
	The AE is considered likely to be related to an etiology other than the
	use of the IP; that is, there are no facts [evidence] or arguments to
	suggest a causal relationship to the IP.
Possibly	The administration of the IP and the occurrence of the AE are
Related	reasonably related in time
	AND
	The AE could be explained equally well by factors or causes other
	than exposure to the IP.
Probably	The administration of IP and the occurrence of the AE are reasonably
Related	related in time
	AND
	The AE is more likely explained by exposure to the IP than by other
	factors or causes.

The following summary tables will be provided:

1. An overview of TEAEs including the number of TEAEs, related TEAEs, TESAEs, related TESAEs, TEAEs leading to premature discontinuation, TEAEs leading to hospitalization, life-threatening TEAEs, number of patients with at least one TEAE, at least one related TEAE, at least one TESAE, at least one TEAE leading to premature discontinuation, at least one TEAE leading to hospitalization, at least one life-threatening TEAE, and at least one TEAE leading to death

- 2. Summary of all TEAEs by treatment group, Primary SOC and PT
- 3. Summary of all related TEAEs by treatment group, Primary SOC and PT
- 4. Summary of all TESAEs by treatment group, Primary SOC and PT
- 5. Summary of all related TESAEs by treatment group, Primary SOC and PT
- 6. Summary of all TEAEs leading to hospitalization by treatment group, Primary SOC and PT
- 7. Summary of all life-threatening TEAEs by treatment group, Primary SOC and PT
- 8. Summary of all TEAEs leading to premature discontinuation by treatment group, Primary SOC and PT
- 9. Summary of all TEAEs by treatment group, Primary SOC and PT and maximum severity

The following individual data listings will be produced:

- 1. A listing of all TEAEs
- 2. A listing of all TESAEs
- 3. A listing of all IMP related TEAEs
- 4. A listing of all IMP related TESAEs
- 5. A listing of all TEAEs leading to hospitalization
- 6. A listing of all life-threatening TEAEs
- 7. A listing of TEAEs leading to premature discontinuation
- 8. A listing of all TEAEs leading to death
- 9. A listing of all AEs started before the first dose of study drug intake
- 10. A listing of all AEs started after the first dose of study drug intake but before the date of randomization (Day 0)

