#### 10.12.4 Physical Examination

Summary analysis will involve the SAF analysis set.

A complete physical examination is to be performed at Screening, Days 0, and Day 28.

These assessments will be summarized by sequence and period using counts and percentages.

All verbatim terms reported in the Physical Examination form will be assigned to a Preferred Term (PT) and will be classified by the primary System Organ Class (SOC) according to the Medical Dictionary for Regulatory Activities (MedDRA) thesaurus, version 23.

A summary table containing the frequency and percentage of patients who exhibited at least one abnormality as well as of the abnormalities reported at Screening, Day 0 and Day 28 by primary SOC and PT will be prepared by treatment sequence.

Physical examination abnormalities will be listed for all patients.

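### Adverse events that begin in the open-label run-in and do not worsen or recur after randomization enter no AE summary table, so the amifampridine column can understate the reactions patients have on drug

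*SAP*

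**What the plan says.** SAP 10.12.1 defines a TEAE as "any AE that emerges after randomization having been previously absent, or worsens relative to the previous periods" and assigns it to the treatment at onset. A later sentence lets an event re-enter if it worsens in a subsequent period or "recurs after having resolved at a previous period; in each of these situations, the TEAE will be considered a new TEAE". The nine summary tables listed there are all tables of TEAEs or serious TEAEs, including "Summary of all TEAEs leading to premature discontinuation by treatment group, Primary SOC and PT". Events that start between the first open-label dose and Day 0 get data listing 10 and no AE summary table.

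The safety population (SAP 10.1) is wider: it "includes subjects who begin the Run-in period regardless of whether they are randomized to double blind medication on Day 0". The safety objective, listed first among the primary objectives in SAP 5.1, is tolerability compared with placebo. The Safety Analysis paragraph of the protocol synopsis limits the safety analysis to TEAEs. The protocol has no TEAE definition of its own.

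Under Protocol 12.2, patients reach Day 0 only after titration on open-label amifampridine to the maximal tolerable dose and at least 7 further days on a stable dose.

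**The concern.** Titration is when a patient first meets the drug and its dose-related reactions. The TEAE rule starts counting after that stage and treats the on-drug state at Day 0 as the reference. A reaction that is already there and stays the same is neither previously absent nor worse, so it is not counted while the patient takes blinded amifampridine. Patients who leave the run-in because of an adverse event belong to the safety population, yet they cannot contribute to any AE table, including the one on discontinuations.

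At stake is how the amifampridine-versus-placebo tolerability tables are read. A low row for a known reaction could reflect the counting rule and not its absence on drug. The analysis is descriptive, so the harm is a misleading summary and not a wrong test.

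**Working it through.** The documents give no AE rate or figure that depends on this rule, so there is nothing to reproduce. The check traces the rule and then illustrates it.

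**Trace of a reaction that began in the run-in** (AP = amifampridine then placebo; PA = placebo then amifampridine; SAP 5.2)

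| Course | Counted under amifampridine? |
|---|---|
| Run-in dropout | No |
| Resolved in the run-in, never returns | No |
| AP, continues unchanged in Period 1 | No |
| Either sequence, on drug, worse than in all previous periods | Yes |
| PA, stops on placebo, returns at the same level in Period 2 | Unclear |

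The PA case is unclear for two reasons. The event is worse than in the placebo period but not worse than in the run-in, and the definition refers to previous periods in the plural. The recurrence sentence speaks of a TEAE that recurs, and the run-in event was never a TEAE.

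**Illustrative counts**

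- N = 12, with 6 per sequence (SAP 6.1).
- Reaction rates of 43% for oral and 26% for peripheral paresthesia come from the food-effect study in healthy volunteers (Protocol 7.4.1). Each subject there received 20 mg on two occasions, so these are study-level rates and not per-dose rates.
- Assumption: the reaction starts in the run-in, persists unchanged on drug and stops on placebo.

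Patients with the reaction on amifampridine = 12 × rate: 12 × 0.43 = 5.2 and 12 × 0.26 = 3.1.

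Counted on the strict reading: 0 and 0.

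Counted if recurrence covers PA = 6 × rate: 6 × 0.43 = 2.6 and 6 × 0.26 = 1.6.

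Capture is therefore 0% to 50%. If a quarter of the reactions worsen on drug after randomization (assumption), the oral-paresthesia count is 5.16 × 0.25 = 1.3 on the strict reading. It is 2.58 + 0.25 × 2.58 = 3.2 with recurrence, so capture is 25% to 62%.

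**Effect on the any-event comparison**

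Let r be the share of patients with a reaction on drug, f the share of those reactions missed by the rule, p the background any-event share under both treatments, and w the share with loss of benefit recorded as a placebo TEAE. With independent causes,

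excess on amifampridine = (1 − p)[r(1 − f) − w].

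Take r = 20/46 = 0.435. Assume p = 0.20 and w = 0:

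| f | Excess (percentage points) |
|---|---|
| 0 | 0.80 × 0.435 = 34.8 |
| 25% | 26.1 |
| 50% | 17.4 |
| 75% | 8.7 |
| 100% | 0 |

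If recurrence covers PA patients, f cannot exceed about 50%, and the last two rows drop out. At f = 50%, w = 1/12 gives 0.80 × (0.217 − 0.083) = 10.7 points, and w = 2/12 gives 4.1. The excess then stays positive unless more than 12 × 0.217 = 2.6 patients have such a placebo event. Only r comes from the documents. Across f, the table runs from no loss to complete loss, so it shows direction and mechanism and does not estimate the size.

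**The case against.** Counting from randomization is defensible. It restricts the tables to the blinded, randomized comparison, and with about 12 randomized patients listing 10 can be read patient by patient. Nothing is hidden, because SAP 10.12 has all observed safety data listed. This stands, and it is why the new-or-worsened count should stay. It does not give a summary of what patients experience on amifampridine after weeks on the same drug.

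Four stronger readings are tempting, and the documents do not support them.

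- A reader might infer that no run-in reaction can reach a TEAE table. The definition itself admits events that worsen, and PA recurrences may qualify.
- A reader might infer that run-in dropouts are counted nowhere. SAP 10.10.1 plans numbers and percentages of premature dosing discontinuations with the primary reason, by period and treatment. Whether the run-in is one of those periods is not stated, so the firm statement is that these patients are in no AE table.
- A reader might infer that returning weakness will inflate the placebo column. SAP 10.12.1 makes worsening of a pre-existing condition reportable, and Protocol 9.6.6 says of physical-examination findings that "Clinically significant changes from baseline will be recorded as AEs". However, no text tells sites to record loss of benefit as an adverse event. The Day 0 baseline in SAP 10.2 ("Change From Baseline (CFB) will be summarized for efficacy and safety assessments, where Baseline is defined as Day 0") governs change-from-baseline summaries and is not a rule for recording events. The examination takes place after randomization only at Day 28 ("A complete physical examination is to be performed at Screening, Days 0, and Day 28"), when only AP patients are on placebo. The route is possible but not prescribed.
- A reader might take 43% as a forecast. It comes from healthy volunteers given 20 mg, the trial's maximum single dose, whereas Protocol 12.2 titrates from 15 mg/day. Protocol 7.4.3 describes the common events as typically transient, so a large missed share is not the natural default.

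**Conclusion.** The point holds in a bounded form. Run-in events that do not worsen or recur after randomization, including those of run-in dropouts, enter no AE summary table and appear only in listing 10. This is firm for AP patients whose reaction continues and for run-in dropouts. For PA patients whose reaction stops on placebo and returns on drug, the text is ambiguous. The omission can only lower the amifampridine column, in a comparison that serves a primary objective.

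The documents do not determine by how much. The counts of 0 to 2.6 out of 5.2 rest on a healthy-volunteer rate and on assumed persistence without worsening. The any-event figures also need assumed values for the missed share, the background rate and placebo loss of benefit. The change is worth making because it is cheap and improves a descriptive summary. The point does not put any test at risk.

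**What to change.** In SAP 10.12.1 and the table shells:

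1. Add an open-label run-in column, covering all safety-population patients and all events starting or worsening after the first open-label dose. Put it in the overview, SOC/PT, related, serious, discontinuation and maximum-severity tables.
2. Keep the new-or-worsened count for the double-blind periods. State that a run-in event counts as a TEAE if it resolves and recurs after randomization, or worsens relative to the immediately preceding period.
3. Beside that count, show the number of patients with each event present during each double-blind treatment, including continuing events. Read the tolerability comparison from both counts.

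Flagging terms that reflect SMA worsening at the blind data review is optional and supportive only.

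The cost is SAP wording and some extra table columns. Non-serious events are already collected from run-in Day 1 (Protocol Table 1, footnote h), resolution dates are already recorded (Protocol 10.1), and SAP section 4 allows revision before the unblinded analyses. The downsides are reliance on stop dates and the chance that a drug-onset event is carried into the placebo column. Ignoring events that end on the first day of a period limits this, and the 1.8-hour half-life in Protocol 7.4.1 suggests that most carry-over would be short.

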A Phase 1 open-label, randomized, single-dose, 2-treatment, 2-period crossover study in 46 healthy volunteers evaluated whether food consumption significantly affected the bioavailability of amifampridine phosphate tablets (LMS-001). Each subject received 20 mg amifampridine phosphate on 2 occasions, once fasting and once after consumption of a standard high fat breakfast. Each single 20 mg dose of amifampridine phosphate were administered 6 days apart. The results from this study indicate co-administration with food reduces exposures determined by C_{max} and AUC by approximately 40% and 20%, respectively. In addition, the time to maximum serum concentrations (T_{max}) was increased 2fold from approximately 38 minutes (fasted) to 78 minutes (fed). The drug was well tolerated with no serious adverse events and only 1 severe event, an episode of gastroenteritis unrelated to amifampridine. The most common AEs occurring in $\geq 10\%$ of subjects were: oral paresthesia (20 subjects; 43%), peripheral paresthesias (12; 26%), dizziness (5; 11%), headache (5; 11%), and oral hypoesthesia (5; 11%). Abdominal pain, nausea, peripheral paresthesias, dizziness, and headache were more commonly reported by subjects following administration of amifampridine phosphate in the fasted state. In humans, amifampridine is exclusively metabolized to a single major metabolite, 3-N-acetyl amifampridine, via N-acetyl transferases (NAT) (Catalyst internal in vitro and in vivo studies; data available upon request). There are 2 NAT enzymes, NAT1 and NAT2, both of which are principally hepatic and both of which are highly polymorphic. These allelic variations lead to slow and fast metabolic rates, which have been well characterized in the Caucasian and Asian populations, but somewhat less well in African populations (Sabbagh, 2006). Slow acetylators are estimated to comprise 50% to 59% of the Caucasian population, with the remainder being rapid acetylators (fast + intermediate). Fast acetylators are over represented in Asian population (92% of Japanese and 80% of Chinese) while they may be under represented in

African populations (25%) (Cascorbi, 1995). Slow acetylators will accumulate drug to higher levels (i.e. higher C_{max}) and clear drug more slowly (i.e. longer $t_{1/2}$), both of which may increase the risk of drug related toxicity (Fukino, 2008; Jetter, 2009).

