# 5 Trial Design

## 5.1 Study Objectives

The primary objectives of the study are:

• To characterize the overall safety and tolerability of amifampridine compared with placebo in patients with SMA Type 3; and

 To assess the clinical efficacy of amifampridine compared with placebo in ambulatory patients with SMA Type 3 based on change from baseline in the Hammersmith Functional Motor Scale Expanded (HFMSE) scores.

The secondary objective of the study is to assess the clinical efficacy of amifampridine compared with placebo by using the change from baseline in six-minute walk test, timed tests, and quality of life assessments:

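### The SAP's TEAE rule can under-count amifampridine reactions that began in the open-label run-in and continue into the blinded periods

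*SAP*

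**What the plan says.** SAP 10.12.1 sets the definition: "A treatment-emergent adverse event (TEAE) is any AE that emerges after randomization having been previously absent, or worsens relative to the previous periods". Attribution follows onset: "All treatment-emergent adverse events (TEAEs) will be summarized by the treatment at the time of onset". There is an exception for worsening and recurrence: "TEAEs will summarized only for the treatment at onset unless it worsens at subsequent period(s) or recurs after having resolved at a previous period". In either case the event is treated as a new TEAE.

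All nine AE summary tables in SAP 10.12.1 are TEAE tables. AEs that start between the first open-label dose and Day 0 appear only in a listing. SAP 10.2 presents safety summaries by sequence, "except for tables related to incidence of AEs which will be presented by treatment group".

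On the design, Protocol 9.1.1 and 12.2 have every patient titrated on open-label amifampridine, held on a stable dose for at least 7 more days, and randomized on Day 0 while still taking it. There is no washout before Period 1 or between the periods.

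The first-listed primary objective in SAP 5.1 is: "To characterize the overall safety and tolerability of amifampridine compared with placebo in patients with SMA Type 3".

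**The concern.** The definition takes randomization as its reference point, but first exposure to the drug comes weeks earlier. A reaction already present on Day 0 was not absent before randomization, and if it continues unchanged it has not worsened. In sequence AP, Period 1 is simply more of the same drug, so such a reaction leaves no trace in the amifampridine column even though the patient has it on blinded amifampridine.

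In sequence PA the reaction may stop on placebo in Period 1 and return on amifampridine in Period 2. Whether it then counts depends on two points the SAP leaves open: whether run-in is a previous period for the recurrence clause, and whether that clause covers an AE that was never itself a TEAE.

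For drug reactions the error runs one way. A reaction that stops on placebo costs the placebo column nothing, while one that persists on amifampridine is dropped from the amifampridine column. At stake is the randomized comparison behind a primary objective. Adding run-in counts alone would not repair it, because the blinded columns would stay as they are.

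**Working it through.** The documents state no AE rate for SMA patients and no carried-in share, so there is no figure to reproduce. The check traces the rule and then applies a counting model.

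**The rule applied to a drug reaction with onset in run-in**

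| Course after Day 0 | AP (amifampridine in Period 1) | PA (amifampridine in Period 2) |
|---|---|---|
| Continues unchanged on amifampridine | Not a TEAE | Not applicable: placebo comes between |
| Worsens on amifampridine | TEAE, amifampridine | TEAE, amifampridine |
| Resolved earlier, returns on amifampridine | TEAE only if the recurrence clause covers run-in AEs | Same condition |

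**Model.** Inputs: 6 patients per sequence (SAP 6.1). Assumptions, none given in the documents:
- f: share of reactions on blinded amifampridine that first arose in run-in
- s: chance that such a reaction is counted in AP
- r: chance that it is counted in PA (it stops on placebo, returns on amifampridine, and the return is accepted as a TEAE)

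Counted/true = [6((1−f) + f·s) + 6((1−f) + f·r)] / 12 = (1−f) + f(s+r)/2.

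| f | s | r | Counted/true |
|---|---|---|---|
| 1 | 0 | 1 | 0 + 1 × 0.5 = 0.50 |
| 0.5 | 0 | 1 | 0.5 + 0.5 × 0.5 = 0.75 |
| 0.25 | 0 | 1 | 0.75 + 0.25 × 0.5 = 0.875 |
| 1 | 0.2 | 1 | 1 × 0.6 = 0.60 |
| 1 | 0 | 0.5 | 1 × 0.25 = 0.25 |
| 0.5 | 0 | 0 | 0.5 + 0 = 0.50 |
| 1 | 0 | 0 | 0.00 |
| any | 1 | 1 | 1.00 |

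**In patients, as illustration only.** Protocol 7.4.1 reports oral paresthesia in 20 of 46 healthy volunteers (43%) and peripheral paresthesia in 12 of 46 (26%), each volunteer having taken single 20 mg doses fasted and fed. These are not SMA rates. With s = 0:
- At 43%: 12 × 0.43 = 5.2 true. Counted: 2.6 (f = 1, r = 1), 3.9 (f = 0.5, r = 1), 2.6 (f = 0.5, r = 0) or 0 (f = 1, r = 0).
- At 26%: 12 × 0.26 = 3.1 true. Counted: 1.6, 2.3, 1.6 or 0 in the same order.

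**Check on the remedy.** A presence table that credited every AE ongoing at Day 0 to the Period 1 treatment would not do. Take f = 1, 43%, and reactions that stop on placebo. Amifampridine would show 5.16/12 = 43%. Placebo would show the 6 × 0.43 = 2.58 carried into PA Period 1, or 2.58/12 = 21.5%, a difference of 21.5 points. The present rule with PA recurrences counted shows 2.58/12 = 21.5% against 0%, also 21.5 points. If instead a carried-in AE must outlast a short interval on the new treatment, the table shows 43% against 0%, and the ratio is 1.00.

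**The case against.** - **Counting new events by treatment at onset is a defined convention, and the safety analysis is descriptive (Protocol Synopsis).** This stands as a reason to keep the TEAE tables. It does not make them sufficient when all patients are exposed to the drug before the reference point.
- **A reader might infer that a carried-in reaction never counts in AP.** The text does not support that. A reaction that worsens is a TEAE, and one that resolved in run-in and returns may be.
- **A reader might infer that the amifampridine rate is roughly halved.** That is one scenario (f = 1, s = 0, r = 1), not a finding. Protocol 7.4.3 calls the common reactions typically transient, so many may be over by Day 0. A reaction gone for good by then is not part of the loss.
- **The contrast between AP and PA depends on reading.** If the recurrence clause is confined to TEAEs and prior absence is read strictly, an unchanged carried-in reaction is lost in both sequences. The sequence difference disappears, but the under-count becomes larger.
- **Placebo loses events too.** Non-drug AEs ongoing at Day 0 are excluded under both treatments, and a TEAE that starts on amifampridine in AP and persists unchanged into placebo counts only for amifampridine. So it cannot be said that the placebo column is untouched. The one-sided loss concerns drug reactions.
- **The listings show it.** Run-in AEs are listed, and the listing order in SAP 14 includes sequence. With about 12 patients, individual cases can be traced. That helps a careful reader but does not correct the summary tables.

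**Conclusion.** The concern holds in limited form. As written, SAP 10.12.1 leaves out of the amifampridine column any reaction that began in run-in and continues unchanged on blinded amifampridine in AP, and it does not settle whether the same reaction counts on re-exposure in PA. For drug reactions this lowers the amifampridine rate and favours amifampridine against placebo.

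The size is unknown. Across all values of f, s and r the counted/true ratio runs from 0 to 1. With no AP carry-in counted, the AP sequence alone can cost up to one half, and more is lost if PA recurrences do not count. There is no loss only if no reaction is carried in or every carried-in reaction is counted. A fixed halving, a total loss in AP, or a placebo column free of any loss would each go beyond what the documents support. The point should be settled before unblinding.

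**What to change.** In SAP 10.12.1:

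1. Keep the TEAE tables.
2. Add a table by SOC and PT, by double-blind treatment and by sequence, of patients with an AE present during that treatment's period, whether new or ongoing from before.
3. Count an AE ongoing at Day 0 or at the Day 14 switch under the new treatment only if its recorded stop date shows it still present beyond a short pre-specified interval after the first dose of that treatment, for example still ongoing the day after the switch. Protocol 7.4.1 gives a mean half-life of 1.6 to 1.8 hours, so 24 hours is about 13 half-lives (24/1.8). The same section says slow acetylators clear the drug more slowly, which should be weighed when the interval is set.
4. State that a run-in AE which resolves and returns after randomization counts as a TEAE under the treatment taken when it returns.

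The cost is SAP wording and one or two extra tables. No new data are needed: non-serious AEs are collected from Day 1 of run-in (Protocol Table 1) and resolution dates are recorded (Protocol 10.1). SAP 4 already provides for review and revision before unblinded analysis. The downside is that long-lasting unrelated AEs will appear under both treatments.
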